### 10.2.3 Injection Site Evaluation

Injection site evaluation (described in [Section 3.5.6](#)) at each visit will be summarized using descriptive statistics.

Injection site evaluation will be presented by patient in a data listing. The listing will show the date of evaluation, indicator if patient was evaluated, reason evaluation was not performed, reaction, finding, indicator if clinically significant, length (mm), and width (mm).

#### **10.2.4 Dose Level Changes**

Any dose level changes that occur throughout the study will be captured in a data listing. For each patient, the visit, reason for dose level change, date of new dose, new dose level (mg), and planned location for injection will be presented.

### **10.3 Adverse Events**

An Adverse Event (AE) is any untoward medical occurrence in a patient or clinical study patient, temporally associated with the use of study treatment, whether or not considered related to the study treatment. An AE can therefore be any unfavorable and unintended sign (including an abnormal laboratory finding), symptom, or disease (new or exacerbated) temporally associated with the use of study treatment. Adverse events, including SAEs, will be collected from the provision of informed consent until the End of Study (EOS) visit (Visit 7). All AEs reported will be coded using the MedDRA version in force at the time of database freeze) and classified by MedDRA SOC and PT. The MedDRA version used for the coding will be noted as a footnote in the tables and listings.

All AEs will be presented by patient in a data listing. The listing will show the verbatim term, MedDRA SOC, MedDRA PT, event start date, event end date (or ongoing), SAE indicator, severity, relationship to study drug, action taken with study drug, action taken, and outcome.

#### **10.3.1 Overview of Adverse Events**

An overview summary table of AEs will be provided, including the number and percentage of patients reporting an AE for the following categories:

- Patients with at least one AE
- Patients with at least one treatment-emergent AE (TEAE)
- Patients with at least one TEAE related to study drug
- Patients with at least one TEAE leading to drug discontinuation
- Patients with at least one TEAE leading to study discontinuation
- Patients with at least one serious AE (SAE)
- Patients with at least one serious TEAE (SAE) related to study drug
- Patients with at least one serious TEAE
- Patients with AE resulting in death on study
- Patients who did not have an AE

### **10.3.2 Treatment-Emergent Adverse Events**

A TEAE is any AE that begins or worsens in intensity on or after the date of the first administration of study drug. Summaries of TEAEs (including number and percentage of patients) will be displayed by the following:

- All TEAEs by MedDRA SOC and PT
- Treatment-emergent SAE by MedDRA SOC and PT

The number and percentage of patients who experienced at least one of the events listed above will be summarized overall and for each SOC and each PT. System organ class and PTs will be presented in descending frequency first and then alphabetically if there are ties. Each patient will contribute at most one count per summarization category. In other words, if a patient has more than one TEAE with same PT, the patient will be counted only once for that PT. Similarly, if a patient has more than one TEAE for a SOC, the patient will be counted only once in that SOC and PT.

### **10.3.3 Severity of the Adverse Event**

Treatment-emergent AEs will also be summarized by severity and will follow the same methods specified in [Section 10.3.2](#). The severity of the TEAE is classified into the five Common Terminology Criteria for Adverse Events (CTCAE) categories of Mild, Moderate, Severe, Life Threatening or Disabling, and Death. If a patient has multiple occurrences of the same MedDRA SOC or PT, then only the most severe event will be summarized in the tables for that SOC and PT. If the severity assessment is missing, the severity of 'Severe' will be assumed.

### **10.3.4 Relationship to Study Drug**

Treatment-emergent AEs will also be summarized by relationship to study drug and will follow the same methods specified in [Section 10.3.2](#). The relationship of the TEAE is classified into two categories of Related and Not Related. If the relationship assessment is missing, the relationship will be considered related. Related TEAEs will also be summarized by MedDRA SOC, PT and maximum severity (defined in [Section 10.3.3](#)).

### **10.3.5 Death, Serious Adverse Events, Adverse Events Leading to Discontinuation**

Serious TEAEs, TEAEs leading to death, and TEAEs leading to study drug discontinuation will be summarized, in separate summary tables, by MedDRA SOC and PT, following the same methods specified in [Section 10.3.2](#). Furthermore, serious TEAEs will also be summarized, separately, by MedDRA SOC, PT, maximum severity/relationship/ relationship and maximum severity (defined in [Section 10.3.3](#) and [10.3.4](#)).

Additionally, separate patient listings also will be provided for the following: patient deaths, serious adverse events, and adverse events leading to study discontinuation and drug discontinuation.

The patient death listing will include any AEs that lead to an outcome of death, and will show the verbatim term, MedDRA SOC, MedDRA PT, event start date, date of death, severity, relationship to study drug, action taken with study drug, action taken, and outcome.

[figure not shown]
The SAE listing will include any AEs that are classified as an SAE, and will show the verbatim term, MedDRA SOC, MedDRA PT, event start date, event end date (or ongoing), SAE category, severity, relationship to study drug, action taken with study drug, action taken, and outcome.

The AEs leading to discontinuation listing will include any AEs that lead to an outcome of discontinuation or study drug withdrawn, and will show the verbatim term, MedDRA SOC, MedDRA PT, event start date, event end date (or ongoing), SAE indicator, severity, relationship to study drug, and outcome.

## 10.4 Clinical Laboratory Data

Hematology, clinical chemistry, and urine analysis laboratory assessments, not discussed below in [Section 10.4.1](#), collected at each study visit and the changes from baseline to any post-baseline visit will be summarized by descriptive statistics. All laboratory tests will be compared to their laboratory normal range. Values outside of the normal range will be further classified as: Low – CS, High – CS, Low – Non-clinically Significant (NCS), High – NCS. Additionally, a shift table will be created to present any change from baseline in normal ranges in all laboratory tests across all post-baseline visits. This table will show the number and percentage of patients who had values that shifted from low - CS, low-NCS, normal, high – NCS, or high-CS at baseline to low - CS, low-NCS, normal, high – NCS, or high-CS at each post-baseline visit. Percentage of patients will be calculated using the number of patients with a baseline value and a non-missing value at the specified post-baseline visit as the denominator.

All laboratory data will be presented in data listings as collected. The listings will show the sample date, laboratory test, indicator test was not done (if applicable), reason test was not done (if applicable), laboratory value, and the change from baseline. Values outside of the reference range will be flagged with 'H' for high and 'L' for low, respectively.

- [REDACTED]
- [REDACTED]
- [REDACTED]

## 10.5 Vital Signs

The aggregated vital signs (described in [Section 3.5.1](#) and [3.5.2](#)) at each study visit and the changes from baseline to any post-baseline visit will be summarized using descriptive statistics.

Vital signs will be presented in a listing. The listing will show the assessment date, vital sign, indicator measurement was not done (if applicable), measurement value, and the change from baseline. Values will include both the triplicate measurements and their aggregated value, where applicable.

## 10.6 Electrocardiograms

The ECG measurements (described in [Section 3.5.4](#)) at Visit 2 (pre and post-dose), Visit 3, Visit 6, and the changes from pre-dose baseline will be summarized descriptively at each visit. In addition, a shift table will be created to show any change from pre-dose baseline to each visit in the overall ECG interpretation.

QTcF interval prolongation will be presented separately as well. The number and percentage of patients with a QTcF interval of >450 msec, >480 msec, and >500 msec will be summarized by visit, along with the number and percentage of patients with a change from pre-dose baseline in QTcF interval of 30 - < 60 msec and  $\geq 60$  msec.

All ECG results will be presented in a data listing. The listing will show the assessment date, ECG measurement, indicator ECG was not done (if applicable), reason ECG was not done (if applicable) ECG value, the change from baseline.

## 10.7 Other Safety Endpoints

### 10.7.1 IWQOL-Lite-CT

The four composite scores (described in [Section 3.5.9](#)), and change from baseline to 16 weeks of treatment in the four composite scores will be presented descriptively. The composite scores and change from baseline composite scores will be presented using mean, SD, minimum, maximum, and median statistics.

The IWQOL-Lite-CT will be presented by patient in data listings. The listings will include study visit and/or study day, the individual item responses, the four composite scores, and change from baseline for the four composite scores.

### 10.7.2 PHQ

The total score (described in [Section 3.5.10](#)) and change from baseline to 16 weeks of treatment in total score will be presented descriptively. The total score and change from baseline total score will be presented using mean, SD, minimum, maximum, and median statistics.

The PHQ will be presented by patient in data listings. The listings will include study visit and/or study day, the individual item responses, total score, and change from baseline for the total score.

### 10.7.3 C-SSRS

The individual questionnaire items (described in [Section 3.5.11](#)) will be presented descriptively at each visit. The individual responses will be presented in frequency tables. Additionally, a shift table of individual questionnaire items will be created to present any change from baseline in item responses across all post-baseline visits. The table will show the number and percentage of patients who had values that shifted from baseline item responses to each post-baseline visit item response. Percentage of patients will be calculated using the number of patients with a baseline value and a non-missing value at the specified post-baseline visit as the denominator.

The C-SSRS will be presented by patient in data listings. The listings will include study visit and/or study day and item responses.

### 10.7.4 SF

The two summary scores (described in [Section 3.5.12](#)), and change from baseline to 16 weeks of treatment in the two summary scores will be presented descriptively. The

summary scores and change from baseline summary scores will be presented using mean, SD, minimum, maximum, and median statistics.

The SF will be presented by patient in data listings. The listings will include study visit and/or study day, the individual item responses, the two summary scores, and change from baseline for the two summary scores.

#### **10.7.5 EQ-5D**

The VAS (described in Section 3.5.13) and change from baseline to 16 weeks of treatment in the VAS score will be presented descriptively. The VAS score and change from baseline in VAS score will be presented using mean, SD, minimum, maximum, and median statistics.

The EQ-5D will be presented by patient in data listings. The listings will include study visit and/or study day, the individual item response, VAS, and change from baseline for the VAS score.

### **11 Statistical/Analytical Issues**

#### **11.1 Handling of Missing Data**

In general, the number of patients with missing values will be summarized and reported as appropriate in all outputs. Calculations for all questionnaires will follow the methods specified in the specific sections of this SAP for the handling of the data.

For primary and key secondary analyses, missing data for Week 16 body weight and BMI will be imputed using LOCF. With the LOCF imputation method, if a patient is missing their Week 16 assessment, their last non-missing assessment will be used. Given that BMI will be calculated using patient's weight and height measurements, if height is missing for any analysis visit, height will be imputed using LOCF.

The primary analysis may be repeated using multiple imputation (MI) as a sensitivity analysis as needed. If performed, MI methods are specified in [Section 16.5](#).

#### **11.2 Handling of Missing/Partial Dates**

While every effort will be made to obtain full, complete information on all data collected Table 4 outlines the imputation rules to be followed for any missing dates. Dates will be presented as collected in the listings.

**Table 4 Imputation Criteria for Missing/Partial Dates**

Variable	Missing Day	Missing Month or Day and Month	Missing Year, Month and Year, or Day and Year	Missing Day, Month, Year
Adverse Event/Medication Start Date	Assign to the first of the month (i.e. UNK-JAN-2019 becomes 01-JAN-2019)	Assign to the month of 'June' (i.e. 01-UNK-2019 becomes 01-JUN-2019), provided the imputed date is on or after the patient's baseline study treatment date; otherwise, the subsequent month after study treatment will be used.	Assign to year of study treatment will be used (i.e. 01-JAN-UNK becomes 01-JAN-2019), provided the imputed date is on or after the patient's study treatment date; otherwise, the subsequent year after treatment will be used.	Assign to baseline study treatment date
Adverse Event/Medication End Date	Assign the last day of the month (i.e. UNK-JAN-2019 becomes 31-JAN-2019).	Assign to the subsequent month after the start date.	Assign to the year of baseline study treatment (i.e. 01-JAN-UNK becomes 01-JAN-2019), provided the imputed date is after the start date; otherwise, the subsequent year after start date will be used.	Assumed medication is ongoing; no imputation

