9.19.1. Time Period and Frequency for Collecting AE and SAE Information

All AEs, including SAEs, will be collected from the provision of informed consent until the EOS visit (Visit 7) at the time points designated in the SoA ([Table 1](#)). AEs reported after dosing on Day 1 will be considered TEAEs.

Medical occurrences that begin before the start of study treatment but after obtaining informed consent will be recorded on the Medical History/Current Medical Conditions section of the eCRF not the AE section.

All SAEs will be recorded and reported to the sponsor or designee within 24 hours, as indicated in [Appendix 6](#). The Investigator will submit any updated SAE data to the sponsor within 24 hours of it being available.

Investigators are not obligated to actively seek AE or SAE in former study patients. However, if the Investigator learns of any SAE, including a death, at any time after a patient has been discharged from the study, and he/she considers the event to be reasonably related to the study treatment or study participation, the Investigator must promptly notify the sponsor.

The method of recording, evaluating, and assessing causality of AE and SAE and the procedures for completing and transmitting SAE reports are provided in [Appendix 6](#).

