21. The EQ-5D-5L will be administered to patients  $\geq 16$  years of age. The EQ-5D-Y will be administered to patients  $> 8$  up to  $< 16$  years of age. In patients under the age of 8 years of age will not complete the EQ-measures.
22. Safety laboratory tests will include: complete blood count with differential (platelet count, red blood cell [RBC] count, hemoglobin, hematocrit, neutrophils, lymphocytes, monocytes, eosinophils, basophils) and standard indices (mean corpuscular volume, mean corpuscular hemoglobin, %reticulocytes), chemistry panel (includes sodium, potassium, chloride,  $\text{CO}_2$ , albumin, total protein, glucose, BUN, creatinine, uric acid, AST, ALT, GGT, CPK, alkaline phosphatase, total bilirubin, direct bilirubin, LDH, calcium, phosphorus), and urinalysis with microscopic analysis if positive findings on dipsticks warrant further examination.
23. Blood samples will be collected prior to dose administration in the fasting state for total cholesterol, high-density lipoprotein cholesterol, low-density lipoprotein cholesterol, and triglycerides.
24. Injection site evaluations and scoring (by the clinical staff) will include identification and measurement of areas of erythema, edema, and induration, as well as the presence of localized pain, tenderness, and itching. Additional evaluation data can be collected at any visit in which there are injection site reactions, even if not a time point for formal assessment.
25. Site personnel will call the patient on Day 15 to confirm the proper dose escalation has occurred and to collect AEs.
26. All patients must have evidence of hypothalamic injury on MRI completed within 8 months of Screening. If no MRI is available, then it may be repeated during the Screening Period.
27. Patients/caretakers will draw up and self-administer/administer the drug once daily in the morning beginning the morning of Day 1 and for the duration of dosing. On days with clinic visits, the patients/caretakers will administer the drug in the clinic in the presence of the clinical staff to assure proper technique.
28. Patients/caretakers will return all (the number recorded) used vials to the clinic when they visit, and both clinic-administered study drug as well as outpatient study drug administration will be recorded in a study diary.
29. AEs will be recorded from the time a patient provides informed consent. AEs reported after dosing on Day 1 will be considered TEAEs.

[figure not shown]

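### An AE start date missing only its day is set to the 1st of the month with no first-dose check, so a post-dose AE can fall out of the TEAE tables

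*SAP*

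**What the plan says.** The start-date row of SAP Table 4 covers both AEs and medications. Its four cells work as follows.

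| Missing part | Imputed start date | Tied to first dose? |
|---|---|---|
| Day only | "Assign to the first of the month (i.e. UNK-JAN-2019 becomes 01-JAN-2019") | No |
| Month, or day and month | June, "provided the imputed date is on or after the patient's baseline study treatment date"; otherwise the month following treatment | Yes |
| Year, alone or with the day or month | Year of treatment, with a similar check; otherwise the following year | Yes |
| Everything | "Assign to baseline study treatment date" | Yes |

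SAP 11.2 applies the table to any missing date and keeps dates as collected in the listings.

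Two rules decide whether an AE is treatment-emergent:

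- SAP 10.3.2 uses the onset date: "A TEAE is any AE that begins or worsens in intensity on or after the date of the first administration of study drug".
- Note 29 to the schedule in SAP 16.1 uses the time of reporting: "AEs reported after dosing on Day 1 will be considered TEAEs". Note 29 to Protocol Table 1 and Protocol 9.19.1 say the same.

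Protocol 9.19.1 also states: "Medical occurrences that begin before the start of study treatment but after obtaining informed consent will be recorded on the Medical History" section of the eCRF rather than the AE section. Yet the same section, and SAP 10.3, collect AEs from informed consent.

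**The concern.** The day-only cell is the one place in the row where an imputed start can land before first dose for an event that began after it. This reverses the sensible ordering: an AE whose month and year are known can be excluded, while an AE with no date information is counted.

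An excluded event drops out of the TEAE lines of the overview and out of the TEAE tables by system organ class and preferred term, severity, relationship, seriousness, death and drug discontinuation (SAP 10.3.1 to 10.3.5). Those tables are the main summary of AE frequency and severity, which is a stated secondary endpoint. For events that truly began after dosing, the error can only be an undercount, and it falls at the start of treatment, when dose titration begins.

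The two TEAE rules can also give opposite answers for the same event, and the SAP does not say which governs.

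**Working it through.** **The rule applied.** The table's own example reproduces: January 2019 with the day unknown becomes 1 January 2019. Now take a first dose on 10 March and an AE start known only as March (illustrative dates):

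- Imputed start = 1 March.
- SAP 10.3.2 test: 1 March is before 10 March, so the onset condition fails. The AE is a TEAE only if worsening after dosing is recorded.
- The same AE with no start date is imputed to 10 March and passes.
- Under SAP 16.1 note 29, the AE is a TEAE if it was reported after Day 1 dosing.

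**How often the rule misdates such an event.** The imputed date precedes first dose whenever first dose is not on the 1st. In a 31-day month, count every pair of first-dose day and true onset day with onset on or after first dose:

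- All pairs: 31 + 30 + … + 1 = 496.
- Pairs with first dose on the 1st, where the rule does no harm: 31.
- Misdated pairs: 496 − 31 = 465, or 465/496 = 93.8%, if all pairs are equally likely (assumption).

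This is a share of AEs that already have the day missing and began after dosing in the first-dose month. It is not a share of all AEs.

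**Length of the exposed window.** For first dose on day *d* of a month with *L* days, exposed days = *L* − *d* + 1 for *d* > 1, and 0 for *d* = 1. Averaged over *d*, assuming first doses are spread evenly over the month, this is (*L* − 1)/2.

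| *L* | Mean exposed days | Share of 113 days to Visit 6 | Share of 141 days to Visit 7 |
|---|---|---|---|
| 28 | 13.5 | 11.9% | 9.6% |
| 30 | 14.5 | 12.8% | 10.3% |
| 31 | 15.0 | 13.3% | 10.6% |

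The range is 0 to 30 days, the maximum being first dose on the 2nd of a 31-day month. Study days 113 and 141 are from the schedule. The Visit 7 column applies to patients who do not enter the extension study.

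The Day 15 dose step falls on calendar day *d* + 14. It is inside the window only if *d* ≤ *L* − 14, that is, by the 14th (28 days), 16th (30 days) or 17th (31 days).

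**Effect on a table row.** One affected patient lowers a TEAE row by at most 1/15 = 6.7 points at the planned 15 patients, or 1/20 = 5.0 points at the 20 implied by the sample-size text (10 + 10). This happens only if that patient has no other TEAE in the row.

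**The case against.** The strongest reply is that the gap is narrow. It needs an AE with only the day missing, in the first-dose month, with first dose not on the 1st and no recorded worsening. Sites call on Day 15 and see patients on Day 29, and SAEs must be reported within 24 hours, so month-only onsets may be rare, above all for serious events. The documents give no count. This stands, and it limits the likely effect.

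The affected event also remains visible. SAP 10.3 states: "All AEs will be presented by patient in a data listing". The overview still counts it among all AEs and, where relevant, all serious AEs. The death, SAE and discontinuation listings are not restricted to TEAEs. The endpoint is worded in terms of AEs, and no test uses the TEAE tables. This also stands: the damage is confined to descriptive tables.

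A third reply is that pre-dose occurrences go to Medical History, so every event on the AE form is post-dose. That does not cure the problem. Collection from consent, and separate overview lines for AEs and TEAEs, show that the SAP allows for AEs that are not treatment-emergent. If the reply were right, imputing such an event to a pre-dose date would plainly be a misclassification. The reporting-based rule would rescue these events only if it governed, and the SAP does not say that it does.

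Finally, real pre-dose AEs can fall in the first-dose month, since screening lasts 14 to 56 days, and a first-dose check would count some of them as TEAEs. That is a true cost. It runs in the same conservative direction as the SAP's own rules for a fully missing start date, missing severity and missing relationship.

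**Conclusion.** The point holds. Followed exactly, Table 4 and SAP 10.3.2 together class a post-dose AE with a missing day in the first-dose month as not treatment-emergent, unless first dose was on the 1st or later worsening is recorded. No other SAP text repairs this.

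The reading is firm; the effect on results is not known. The average window of 13.5 to 15.0 days rests on evenly spread first-dose dates and measures calendar time, not the share of AEs. The 6.7-point limit is per affected patient and per row, and the number of affected patients cannot be had from the documents. No efficacy result is touched. The correction is worth making before database lock because the error for truly post-dose events goes in one direction and is cheap to remove.

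**What to change.** Split the AE rule from the medication rule in the day-only cell of Table 4, leaving medication start dates unchanged. Suggested text for AEs:

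> If the day is missing and the month and year equal those of first dose, impute the first-dose date, unless the AE end date is before first dose or the AE is recorded as starting before first dose. Otherwise impute the first of the month.

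The AE items named in SAP 10.3 include no field for onset before or after dosing. The second exception therefore works only if the eCRF or a site query supplies that information; otherwise the end date carries it.

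Reconcile SAP 10.3.2 with note 29 in SAP 16.1, and add to 10.3.2:

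> An AE is treatment-emergent unless its available date parts show onset before first dose without later worsening.

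The cost is one split cell, one reconciled definition with an added sentence, and a line of code. The downside is that a few truly pre-dose events with incomplete dates may be counted as TEAEs.

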### 8.4 Prior and Concomitant Medications

All summaries will be done based on the FAS population. Concomitant medications for this study are defined as any medication the patient is receiving at the time of enrollment, or any new medication received by the patient after the date of enrollment. Prior medications are medications with a stop date prior to date of study enrollment. Medications will be coded using the WHO Drug Dictionary. The versions used for the coding will be noted as a footnote in the tables and listings.

The number and percentage of patients who receive prior and concomitant medications will be summarized, separately, by the WHO Drug Dictionary Anatomical Therapeutic Chemical 4th level (ATC-4) and the preferred name. If the 4th level term is not available, the next available level (e.g., ATC-3) will be used.

ATC-4 and preferred name will be presented in descending frequency first and then alphabetically if there are ties. Each patient will contribute at most one count per summarization category. In other words, if a patient has more than one medication with same preferred name, the patient will be counted only once for that preferred name. Similarly, if a patient has more than one medication for an ATC-4 level, the patient will be counted only once in that ATC-4 level and preferred name.

Prior and concomitant medications will be presented by patient in a data listing. The listing will show the verbatim medication/therapy, the ATC-4 term, preferred name, indication, medication start date, medication end date (or ongoing), dose, dose unit, frequency, and route.

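### Read literally, SAP Table 4 overrides recorded years when the month is missing, which can put a drug in the wrong one of the prior and concomitant medication tables

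*SAP*

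**What the plan says.** SAP Section 11.2, Table 4, has one row for start dates and one for end dates, each covering adverse events and medications together.

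- **Start, month (or day and month) missing.** The first step is "Assign to the month of 'June' (i.e. 01-UNK-2019 becomes 01-JUN-2019". This stands only "provided the imputed date is on or after the patient's baseline study treatment date". Failing that, "otherwise, the subsequent month after study treatment will be used".
- **Stop, month (or day and month) missing.** "Assign to the subsequent month after the start date". The recorded stop year is not mentioned.
- **Stop, only the day missing.** "Assign the last day of the month (i.e. UNK-JAN-2019 becomes 31-JAN-2019", so the recorded month and year are kept.
- **Stop wholly missing.** "Assumed medication is ongoing; no imputation".

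SAP Section 8.4 then uses the stop date to classify: "Prior medications are medications with a stop date prior to date of study enrollment". Concomitant drugs are those in use at enrolment or newly taken afterwards. The two groups are tabulated separately on the Full Analysis Set. Section 11.2 also says that listings show dates as they were collected.

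**The concern.** A date rule should fill in what is missing and leave alone what is known. Two cells of Table 4 appear not to do so. A first-dose floor is a familiar device for adverse events of uncertain onset, where it errs towards calling an event treatment-emergent. Here the same floor applies to medications, many of which can legitimately have started years before the trial. The stop rule then takes its month from a start date that may itself have been moved, and does not use the recorded stop year.

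At stake is the accuracy of the two medication tables. A finished drug could be reported as taken on study, or a drug in use at enrolment could be reported as finished. Either table would then disagree with the as-collected listing in the same report.

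**Working it through.** **Inputs.** The Table 4 rules and the Section 8.4 stop-date rule are as set out above. The protocol synopsis gives 26 Feb 2021 as the estimated first enrolment. First-dose dates of 10-MAY-2021, 15-JUL-2021 and 10-DEC-2021 are assumed for illustration, and enrolment is taken as the day of first dose. Table 4 gives no day for its fallback month; where a day is shown below, the first of the month is assumed.

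**The plan's own examples.** With a hypothetical first dose of 01-JAN-2019 the rules reproduce all four examples in Table 4:
- start UNK-JAN-2019 gives 01-JAN-2019
- start 01-UNK-2019 gives 01-JUN-2019
- start 01-JAN-UNK gives 01-JAN-2019
- stop UNK-JAN-2019 gives 31-JAN-2019

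Under this trial's dates the second example no longer works. With first dose 26-FEB-2021, 01-JUN-2019 precedes treatment, so the fallback gives 01-MAR-2021. The same happens to every year-only start from 2020 or earlier, because June 2020 is already before 26 Feb 2021.

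**Cases on the literal reading, first dose 10-MAY-2021.**

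| Recorded start | Recorded stop | Imputed start | Imputed stop | Class under 8.4 | Class implied by recorded parts |
|---|---|---|---|---|---|
| 2012 | 2014 | June 2021 | July 2021 | concomitant | prior |
| 10-MAR-2012 | 2022 | unchanged | April 2012 | prior | concomitant |
| 2012 | June 2015 | June 2021 | 30-JUN-2015 | prior | prior |
| 2012 | 15-JUN-2015 | June 2021 | unchanged | prior | prior |
| 2012 | wholly missing | June 2021 | ongoing | concomitant | concomitant |
| 10-MAR-2012 | 2015 | unchanged | April 2012 | prior | prior |

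Row 1: 01-JUN-2012 is before 10-MAY-2021, so the start moves to the month after May 2021. The stop goes to the month after that. The errors are 2021 − 2012 = 9 years and 2021 − 2014 = 7 years, and the class changes.

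Row 2: the start is complete and needs no imputation, but the stop still becomes the month after March 2012. This result does not depend on the first-dose date. A stop in 2022 is most plausible for a patient first dosed late in 2021.

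Rows 3 and 4: the class is right, but the imputed start falls after the stop.

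Row 5: only the start year is wrong. Row 6: only the stop year is wrong.

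**Sensitivity to first dose.** A drug recorded as 2012 to 2015 becomes March to April 2021 with first dose 26-FEB-2021, August to September 2021 with 15-JUL-2021, and January to February 2022 with 10-DEC-2021. It is classed as concomitant each time.

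**Alternative reading.** Suppose the fallback supplies only the missing month and the recorded year is kept. With first dose 26-FEB-2021, the 2012 to 2015 drug becomes 01-MAR-2012 to 01-APR-2015 and stays prior. No year is overwritten.

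**Size per error.** With about 15 patients, one misplaced patient moves a percentage by 1/15, or about 6.7 points.

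**The case against.** The strongest reply is that Table 4 need not be read literally. In the column for a missing year, the start-date fallback reads "otherwise, the subsequent year after treatment will be used", which supplies only the missing part. By analogy the month column would supply only a month. That reading is possible, but for a past year it leaves the date before treatment, and so defeats the condition that triggered the fallback. The literal reading fits the text better. At the least, two programmers could produce different tables.

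A second reply is that the data may hardly arise. Protocol Section 7.7 requires recording only of drugs in use at enrolment or taken during the study, so a drug finished in 2014 is not asked for. This limits the first example. It does not remove the point, because SAP Section 8.4 plans a table of prior medications and because the second example concerns a drug that Section 7.7 does cover.

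Three stronger conclusions might be inferred, and the documents support none of them.

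- **Per-protocol membership would change.** Under SAP Section 7, exclusion for a prohibited treatment requires a judged substantial impact on the primary outcome. It follows review of deviation listings before database lock. Nothing there uses an imputed date.
- **Long-term hormone replacement would be reported as newly started.** A drug ongoing at enrolment is concomitant whatever its imputed start. The Section 8.4 tables count patients by drug class and preferred name, without start dates or a split between new and continuing use.
- **Adverse event results would be distorted.** An onset known only as 2022 in a patient dosed in late 2021 becomes 01-JUN-2022, after the estimated study end of 31 Mar 2022. The recorded year is kept, the event is correctly treatment-emergent under SAP Section 10.3.2, and no planned table changes. The study end date is itself only an estimate.

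**Conclusion.** The concern holds as a minor defect. On its literal reading Table 4 replaces a recorded pre-treatment start year and ignores a recorded stop year whenever the month is missing. A drug changes table in two situations: when start and stop are both known only to the year and the drug had finished before enrolment, or when a complete start is paired with a year-only stop that falls after enrolment. With a month-level or complete stop before enrolment the class is right, but the imputed dates run backwards.

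The consequence is limited to the descriptive prior and concomitant medication tables. The efficacy endpoints do not use these dates, and the listings keep the collected ones. The conclusion rests on the literal reading and on assumed first-dose dates. The documents give no basis for estimating how many records have year-only dates.

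**What to change.** Amend Table 4 as follows.

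1. State that a recorded year or month is never changed by imputation.
2. Apply the first-dose fallback only when the recorded parts are compatible with a date on or after first dose, and keep the result within the recorded year.
3. Give medications their own rows: start is the earliest date, and stop the latest date, compatible with the recorded parts, with the stop capped at last contact.

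Under these rules the drug recorded as 2012 to 2014 becomes 01-JAN-2012 to 31-DEC-2014 and is prior. The drug with stop year 2022 has its stop set to 31-DEC-2022 or last contact, whichever is earlier, and is concomitant for a patient enrolled in 2021.

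The cost is a few lines of SAP text and a small edit to the date-imputation program before database lock. No new data are needed.
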